**Pseudocode:**

- DEFINE eventD29 as the binary variable for death or progression to mechanical ventilation or death by Day 29 (1=Yes, 0=No, .=Missing)
- DEFINE input3 as the analysis dataset containing subjects lost to follow-up while hospitalized or transferred with missing event. Add the variable for the probability of an event between last assessment and Day 29 (**pe**) calculated in step 3 to the dataset for subjects with missing data to be imputed.
- DEFINE imp\_out2 as the output dataset containing the 20 imputed datasets

```
data imp_out3;
  set input3;
  subid=input(substr(usubjid,5,4),best12.);
  seed=7564+subid;
  call streaminit(seed);
  p=&pe.;
  do i=1 to 20;
    _imputation_ = i;
    eventd29=rand("Binomial",p,1);
    output;
  end;
  drop p I ;
run;
```

imp\_out3 will have 20 imputed values for each subject who was lost to follow-up while hospitalized or transferred and had missing event.

Combine the 3 output datasets from the three different imputations.

```
data imp_out_all;
  set imp_out1 imp_out2 imp_out3;
run;
```

Create 20 replicates for each subject with non-missing event:

```
data complete_all;
  set complete;
  do i=1 to 20;
    _imputation_ = i;
    output;
  end;
  drop i;
run;
```

The final dataset to be used for analysis will be created by combined imputed data and complete data:

```
data imp_out;
  set imp_out_all complete;
  proc sort; by subject_imputation_;
run;
```

Using this imp\_out dataset, calculate odds ratio follow:

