#### Pseudocode:

- DEFINE eventD29 as the binary variable for death or progression to mechanical ventilation or death by Day 29 (1=Yes, 0=No, .=Missing)
- DEFINE input1 as the full analysis dataset containing all baseline covariates and event indicator for complete data subjects as well as subjects with no post-baseline data with missing event indicator to be imputed.

- DEFINE imp\_out1 as the output dataset containing the 20 imputed datasets

```
proc mi data=input1  out= imp_out1 nimpute=20 seed = 837405 nointprint;
class trtvar baseordscorevar basedexausefl blackhispfl comorb2fl eventD29;
var trtvar baseordscorevar basedexausefl age blackhispfl comorb2fl basecrp eventD29;
monotone logistic(eventD29= trtvar baseordscorevar basedexausevar age blackhispfl
comorb2fl basecrp );
run;
```

The above procedure will output imp\_out1 dataset which contains 20 replicates for each subject. Update the dataset to remove subjects with complete data and only keep the 20 imputed datasets for subjects with no post-baseline data.

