##### Pseudocode:

- DEFINE eventD29 as the binary variable for death or progression to mechanical ventilation or death by Day 29 (1=Yes, 0=No, .=Missing)
- DEFINE input2 as the analysis dataset containing discharged subjects with missing event.
- Define evnrate as the event rate among subjects discharged to a location other than LTAC, hospice care or other hospital who have known outcome.
- DEFINE imp\_out2 as the output dataset containing the 20 imputed datasets

```
data imp_out2;
  set input2;
  subid=input(substr(usubjid,5,4),best12.);
  seed=3849+subid;
  call streaminit(seed);
  p=&evnrate;
  do i=1 to 20;
    _imputation_ = i;
    eventD29=rand("Binomial",p,1);
    output;
  end;
  drop p i;
run;
```

imp\_out2 contains 20 imputed values for each subject discharged to a location other than LTAC, hospice care or other hospital who had missing event.

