#### **Pseudocode:**

- DEFINE input2 as the analysis dataset containing all discharged subjects including those with missing event to be imputed and those with known outcome.

```
proc mi data=input2 out= imp_out2 n impute=20 seed = 748485 noint;
class baseordscorevar eventD29;
var eventD29;
monotone logistic(eventD29= baseordscorevar);
run;
```

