#### Odds ratios from logistic regression using multiple imputation:

```
proc logistic data=imp_out out=imp_parms;
  by _imputation_;
  class baseordscorevar (param=ref ref=5) basedexausevar (param=ref ref=no steroid
use) trtvar (param=ref ref=placebolabel);
  model eventd29 (eventd29='1') = trtvar baseordscorevar basedexausevar age
baseCRP;
  ods output oddsratioswald = orest parameterestimates=pars;
run;

*Keep only estimates for the treatment variable;
data pars1;set pars;where Variable='Treatment variable';run;
*Combine estimates;
PROC MIANALYZE DATA=pars1;
  ODS OUTPUT PARAMETERESTIMATES= logor;
  MODELEFFECTS estimate ;
  STDERR stderr ;
RUN;
*Transform estimates from the log(OR) scale to the OR scale;
data OR;
  SET logor;
  OR_estimate = EXP(ESTIMATE);
```

```

OR_LCL_95 =OR_estimate*EXP (-1.96*STDERR) ;
OR_UCL_95 =OR_estimate*EXP (+1.96*STDERR) ;
OR_LCL_80 =OR_estimate*EXP (-1.28*STDERR) ;
OR_UCL_80 =OR_estimate*EXP (+1.28*STDERR) ;

RUN;run;
    
```

To estimate risk differences from logistic regression, the approach from Ge et. al [1] as described below:

```

proc logistic data = dataset outmodel=pout;
    class trtvar ;
    model surv(event='1') = trtvar othercovariates ;
run;

*Create dataset tempa to contain all subjects and assign them the active Lenzilumab + RDV and dataset tempb which include all subjects assigned the placebo treatment;

proc logistic inmodel=pout;
    score data = tempa out=preda(keep=id P_a rename= (P_1=P_a)) ;
run;

proc logistic inmodel=pout;
    score data = tempb out=predp(keep=id P_1 rename= (P_1=P_p)) ;
run;

proc sort data=preda;by subjectid;run;
proc sort data=predp;by subjectid;run;

*Combine to obtain risk differences in probabilities for each subject;

data comb;
    merge predp preda;
    by subjectid;
    diff=P_a-P_p;
run;

proc means data=comb; var diff; run;
    
```

To obtain the CI for the risk difference, use bootstrap with the following steps:

1. Sample with replacement from the dataset.
2. Obtain risk difference estimate for each bootstrap sample.
3. Repeat this step the above step 1000 times and use the 2.5th and 97.5th percentiles of the risk estimates as the limits for the 95% CI for the risk difference. The risk difference from bootstrap should be equal to the risk difference obtained prior to performing bootstrap.

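### The primary-endpoint imputation code stacks the unreplicated known-outcome file, so as written it does not build the 20 completed datasets that the SAP describes

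*SAP*

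**What the plan says.** SAP Section 6.1 states that the primary endpoint will be analysed by multiple imputation following the pseudocode in Section 6.5. That code is therefore part of the analysis definition.

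The relevant steps are:

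- Section 6.5.1.1 (no post-baseline data) imputes and then trims `imp_out1`: "Update the dataset to remove subjects with complete data and only keep the 20 imputed datasets for subjects with no post-baseline data".
- Section 6.5.1.2 (lost after discharge), in the branch described as expected, starts from missing outcomes only: "DEFINE input2 as the analysis dataset containing discharged subjects with missing event".
- Section 6.5.1.2, in the branch with 10 or more post-discharge events, starts from a file "containing all discharged subjects including those with missing event to be imputed and those with known outcome". No trimming step follows.
- Section 6.5.1.3 (lost while hospitalized or transferred) forms `imp_out3` from missing-outcome subjects only, then stacks the three files as `imp_out_all`.
- The same section goes on: "Create 20 replicates for each subject with non-missing event". The step is coded as "data complete_all", with `_imputation_` running from 1 to 20.
- It then states: "The final dataset to be used for analysis will be created by combined imputed data and complete data". The code for this step is "set imp_out_all complete".
- The logistic regression that follows is run "by _imputation" number, and the treatment estimates go to PROC MIANALYZE.

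**The concern.** `complete_all` is created and never used in the code shown. The file stacked in its place, `complete`, is given no imputation number there. A regression run separately for each imputation number then cannot put observed and imputed subjects in the same fit, and doing so is the whole purpose of the step.

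The stake is the primary odds ratio and p-value. Several other analyses reuse the step: the sensitivity analyses in SAP Section 8.1.2, key secondary endpoint 3 (Section 8.2.3 and Table 2), and the bootstrap interval for the risk difference, which is repeated within each imputed dataset.

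A lesser inconsistency sits in the same block. Step 3 computes an event probability for each subject, and the text adds it to the input file as a variable. The code then reads `p=&pe.`, a macro reference, as if the value were common to all subjects.

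**Working it through.** **The plan's own figure.** SAP Section 5 gives 400 in the subgroup, odds ratio 2.5, two-sided alpha 0.049, and 80% power at a 16% control rate. Allocation is taken as 200 per arm, from the 275:275 split in Section 4.3.

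- Treated odds = (0.16/0.84)/2.5 = 0.0762, so the treated rate is 0.0708.
- Unpooled SE = √(0.16×0.84/200 + 0.0708×0.9292/200) = 0.0316.
- z = 0.0892/0.0316 = 2.82. Power = Φ(2.82 − 1.97) = Φ(0.85), about 80%.
- To one decimal, power is 80.3% unpooled and 79.7% pooled. At a 21% control rate (treated 9.61%) it is 89.2% and 88.7%, against the stated 89%.

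The sample-size figures reproduce. The point does not rest on them; they only supply N = 400.

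**Structure of the final file.** Let N be the subjects in the analysis population and m those with a missing outcome. In the expected branch:

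- As written, `imp_out` has 20m + (N − m) rows. Groups 1 to 20 hold m subjects each. One further group, with missing `_imputation_`, holds the N − m known-outcome subjects.
- With `complete_all`, it has 20m + 20(N − m) = 20N = 8,000 rows, and each of the 20 groups holds N = 400.

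The SAP gives no missing rate; Section 5 says only that little is expected. The rates below are assumptions.

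| Assumed missing | m (size of each numbered group as written) | Subjects in the extra group | Rows as written | Simulated fits that broke down, of 20 |
|---|---|---|---|---|
| 1% | 4 | 396 | 476 | 20 |
| 2% | 8 | 392 | 552 | 19 |
| 5% | 20 | 380 | 780 | 19 |
| 10% | 40 | 360 | 1,160 | 16 |

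The last column comes from simulated data with the planned model terms (treatment, ordinal score, dexamethasone, age, CRP) and assumed covariates; breakdown means separation or non-convergence. A separate simulation with about 12% events and five seeds gave 17 to 19 failures of 20 with 16 imputed subjects, and 14 to 18 with 32. With `complete_all`, all 20 fits converged at every rate in the table, with an SE of the log odds ratio of about 0.32 to 0.34.

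**The extra group.** The filter before PROC MIANALYZE selects the treatment row. It does not exclude the group with missing `_imputation_`, so that group's estimate would be pooled as a 21st result unless someone removed it.

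**The other branch.** With 10 or more post-discharge events, `imp_out2` also carries the discharged subjects with known outcome. Call their number d. As written, each numbered group then holds m + d subjects. Changing only the stacked file name would give N + d rows per dataset, with those d subjects counted twice.

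**The sort.** The sort key appears as `subject_imputation_`, perhaps with a space lost in extraction. Read as one variable, it is not defined in the code shown. Read as subject then `_imputation_`, it leaves the file out of order for a regression by `_imputation_`.

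**The case against.** The block is labelled pseudocode and could not be run literally. It contains placeholders, such as the reference-level labels and the value used to pick out the treatment row, and the sort order alone would stop the regression step. Reading one dataset name literally while repairing everything else is selective.

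The intent is also plain. The replication step has no other purpose, and the tipping-point pseudocode in SAP Section 8.1.3 states the parallel step correctly, combining each of the 20 imputed datasets with all complete-outcome subjects. On `&pe.`, a macro reference is text substitution and could resolve to the variable name, and the prose already requires a subject-level probability.

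Most of this stands. A reader might infer that the plan would silently deliver an invalid primary p-value. The documents do not support that, since the code would more likely halt or fail visibly. A reader might also infer that the numbered fits carry nothing from the observed subjects. That is not right either: the imputed values are drawn from rates or models fitted to observed subjects.

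The label does not make the slip harmless. Section 6.1 adopts this pseudocode for the primary endpoint, and the code fixes seeds, dataset names and the number of imputations. An independent programmer checking against the SAP would be checking against a step that contradicts its own text.

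**Conclusion.** The point holds as a coding error in the definition of the primary-analysis file. In the expected branch, the 20 numbered groups hold only missing-outcome subjects, and all known-outcome subjects sit in one unnumbered group. The group counts depend only on N and m. The breakdown counts are illustrative and rest on assumed missing rates and simulated covariates.

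It is not a flaw in the three-part imputation method, and it leaves no doubt about the intended model. It would also be too strong to say that the imputed analyses always contain only missing-outcome subjects, because the branch with 10 or more post-discharge events brings in known-outcome discharged subjects. The `&pe.` line is a secondary inconsistency. The error should be corrected, but by itself it does not undermine the trial's conclusions.

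**What to change.** 1. In Section 6.5.1.3, stack the replicated file: `set imp_out_all complete_all;`.
2. Sort by `_imputation_`, then subject, so that the regression by imputation number can run.
3. Replace `p=&pe.` with the subject-level variable `pe` from Step 3.
4. In the branch of Section 6.5.1.2 with 10 or more post-discharge events, remove known-outcome subjects from `imp_out2`, as Section 6.5.1.1 already does for `imp_out1`. Without this, change 1 double-counts them.
5. Add a check that each of the 20 datasets contains every subject in the analysis population exactly once. A check for presence alone would miss the duplicates.

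The cost is a few lines of SAP text. No change is needed to the estimand, model, sample size or data collection. If the production program already does this, record that and bring the SAP code into line.

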#### Odds ratios from logistic regression using multiple imputation:

```
proc logistic data=imp_out out=imp_parms;
  by _imputation_;
  class baseordscorevar (param=ref ref=5) basedexausevar (param=ref ref=no steroid
use) trtvar (param=ref ref=placebolabel);
  model eventd29 (eventd29='1') = trtvar baseordscorevar basedexausevar age
baseCRP;
  ods output oddsratioswald = orest parameterestimates=pars;
run;

*Keep only estimates for the treatment variable;
data pars1;set pars;where Variable='Treatment variable';run;
*Combine estimates;
PROC MIANALYZE DATA=pars1;
  ODS OUTPUT PARAMETERESTIMATES= logor;
  MODELEFFECTS estimate ;
  STDERR stderr ;
RUN;
*Transform estimates from the log(OR) scale to the OR scale;
data OR;
  SET logor;
  OR_estimate = EXP(ESTIMATE);
```

```

OR_LCL_95 =OR_estimate*EXP (-1.96*STDERR) ;
OR_UCL_95 =OR_estimate*EXP (+1.96*STDERR) ;
OR_LCL_80 =OR_estimate*EXP (-1.28*STDERR) ;
OR_UCL_80 =OR_estimate*EXP (+1.28*STDERR) ;

RUN;run;
    
```

To estimate risk differences from logistic regression, the approach from Ge et. al [1] as described below:

```

proc logistic data = dataset outmodel=pout;
    class trtvar ;
    model surv(event='1') = trtvar othercovariates ;
run;

*Create dataset tempa to contain all subjects and assign them the active Lenzilumab + RDV and dataset tempb which include all subjects assigned the placebo treatment;

proc logistic inmodel=pout;
    score data = tempa out=preda(keep=id P_a rename= (P_1=P_a)) ;
run;

proc logistic inmodel=pout;
    score data = tempb out=predp(keep=id P_1 rename= (P_1=P_p)) ;
run;

proc sort data=preda;by subjectid;run;
proc sort data=predp;by subjectid;run;

*Combine to obtain risk differences in probabilities for each subject;

data comb;
    merge predp preda;
    by subjectid;
    diff=P_a-P_p;
run;

proc means data=comb; var diff; run;
    
```

To obtain the CI for the risk difference, use bootstrap with the following steps:

1. Sample with replacement from the dataset.
2. Obtain risk difference estimate for each bootstrap sample.
3. Repeat this step the above step 1000 times and use the 2.5th and 97.5th percentiles of the risk estimates as the limits for the 95% CI for the risk difference. The risk difference from bootstrap should be equal to the risk difference obtained prior to performing bootstrap.

To generate bootstrap CI for risk difference using multiple imputation, repeat steps 1 and 2 for each imputed dataset. The final risk difference will be calculated as the mean risk difference across all imputed datasets, and the 95% CI will be obtained as the 2.5th and 97.5th percentile of risk difference estimates across all imputed datasets and bootstrap samples [2].

### 6.5.2. Targeted Maximum Likelihood Method (TMLE)

Missingness in the outcome is easily accounted for in the estimation procedure of TMLE using the missing indicator as shown in the below pseudocode provided that only baseline covariate and treatment information is used in the adjustment for missing data. Because of this requirement, we consider two approaches:

#### First approach:

The first approach uses TMLE with only baseline covariates to adjust for missing data and does not make use of discharge or transfer data for this adjustment. All subjects missing outcome data due to being terminated early from the study or being lost to follow-up before having an event and before Day 29 will be considered as having a missing outcome data and be imputed using the missing indicator in TMLE.

#### Second approach:

The second uses a multiple imputation approach that, as in the multiple imputation analyses described in Section 6.5.1, does make use of the discharge and transfer data. TMLE is used to analyze the individual imputed data sets. Standard methods are then used to combine across results across the imputed data sets. We note that this approach cannot be considered formally to be a TMLE analysis. The reason for the second approach is to assess the impact of not using the post-baseline data in the first approach.

Assumptions for the second approach:

- Discharged subjects missing event will be considered non-events.
- For participants who are censored while hospitalized or after transfer, the multiple imputation approach described in Section 6.5.1.3 will be used.
- Event for subjects with no post-baseline data will be missing and handled using TMLE

Each imputed dataset will be analyzed using TMLE. For patients with no post-baseline follow-up, no imputation is required. We will use the feature in TMLE that permits use of baseline data as part of adjustment for these patients.

The estimates of treatment effects,  $\hat{\theta}$ , are obtained by taking the mean of risk difference estimates across imputations. The variance of these estimates is estimated by the sum of the average variances of estimates within each imputation and  $(m+1)/m$  multiplied by the empirical variance across of the estimates of interest across imputations, where  $m$  is the number of imputations.

**The within imputation variance**,  $V_W$ , is the average variance of risk difference estimates within each imputation and is calculated as:  $V_W = \frac{1}{m} \sum_{i=1}^m SE^2$

**The between imputation variance**,  $V_B$ , reflects the extra variance due to imputation and is obtained by taking the variance of risk difference over imputed datasets. The average variance of risk difference estimates within each imputation and is calculated as:  $V_B = \frac{1}{m-1} \sum_{i=1}^m (\hat{\theta} - \theta_i)^2$  where

$\hat{\theta}$  is the overall mean estimate for risk difference

$\theta_i$  is the risk difference estimate for each imputed dataset.

**The total variance**,  $V_T$ , is then calculated as:  $V_T = V_W + \frac{(m+1)}{m} V_B$

The 95% CI for risk difference can then be obtained by  $(\hat{\theta} - 1.96\sqrt{V_T}, \hat{\theta} + 1.96\sqrt{V_T})$

The same approach will be followed for combining odds ratio estimates from TMLE version with MI and their 95% CI. First, odds ratio will first be transformed on the log scale before calculating the mean log-OR (mlog\_OR) and total variance for for log (OR) (VlogORT). The final OR estimate is then obtained as

$OR = \exp(mlog_{OR})$  and the 95% CI is obtained as  $(OR * \exp(-1.96 * \sqrt{VlogOR_T}), OR * \exp(1.96 * \sqrt{VlogOR_T}))$

These estimates can also be obtained in SAS for risk difference and ORs as shown below:

#### Pseudocode in SAS:

##### Risk difference calculation in SAS after TMLE:

1. Combine transformed estimates from multiple imputed datasets;
  - **rd\_t** is a dataset that has columns for imputation number, risk difference estimates and standard error for risk difference calculated from each imputation dataset
  - **comb\_rd\_t** contains the final combined estimates and standard errors for risk difference

```
PROC MIANALYZE DATA=rd_t;
  ODS OUTPUT PARAMETERESTIMATES= comb_rd_t;
  MODELEFFECTS rd_value ; #risk difference estimates;
  STDERR rd_se; ; #risk difference standard error;
RUN;
```

2. Back-transform combined values to obtain final estimate and 95% CI;

```
DATA comb_rd_bt;
  SET comb_rd_t;
  RD_Estimate = ESTIMATE; *Pooled risk difference;
  RD_LCL =ESTIMATE -1.96*STDERR; *Pooled lower limit;
  RD_UCL =ESTIMATE +1.96*STDERR; *Pooled upper limit;
RUN;
```

##### Odds ratio calculation in SAS after TMLE:

3. Combine transformed estimates from multiple imputed datasets;
  - **logsodds\_t** is a dataset that has columns for imputation number, log(OR) estimates and standard error for log(OR) calculated from each imputation dataset
  - **comb\_logsodds\_t** contains the final combined estimates and standard errors for log (OR)

```
PROC MIANALYZE DATA=logsodds_t;
  ODS OUTPUT PARAMETERESTIMATES= comb_logsodds_t;
  MODELEFFECTS log_or_value ; #log_OR estimates;
  STDERR log_or_se; ; #log_OR standard error;
RUN;
```

4. Back-transform combined values to obtain final estimate for OR and its 95% CI;

```
DATA comb_lgsodds_bt;
  SET comb_logsodds_t;
  OR_estimate = EXP(ESTIMATE); *Pooled odds ratio;
  OR_LCL =OR_estimate*EXP(-1.96*STDERR); *Pooled lower limit;
```

```
OR_UCL =OR_estimate*EXP (+1.96*STDERR); *Pooled upper limit;  
RUN;
```

For both of these approaches, TMLE will be implemented using the tmle R package (<https://cran.r-project.org/web/packages/tmle/index.html>). For the second approach of TMLE that includes MI, final estimates will be combined across the different imputation datasets using either SAS pseudocode provided above or using formulas provides in either R or SAS.

**Pseudo code:**

```
Y = binary outcome variable (that can include missing values)  
trt = treatment information coded as 0, 1  
BaselineCov = Dataframe of baseline covariates (numerical) of each patient.  
MissingIndicator = Vector with 1 indicating that outcome was missing, 0 otherwise  
SL.library = c("SL.glm", "SL.gam", "SL.glmnet")  
  
tmResult = tmle(Y = Y, A = trt, Delta = MissingIndicator, W = BaselineCov, family = "binomial", Q.SL.library = SL.library, g.SL.library = SL.library, Delta.SL.library = SL.library)
```

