### 8.1.3. Secondary Analysis for the Primary Endpoint

A secondary analysis of the primary endpoint will be performed using a targeted maximum likelihood estimate (TMLE) method for binary outcomes that estimates the average treatment effect among the entire population in terms of an odds ratio with corresponding p-value will be used. The test decision for this secondary analysis will be based on the p-value of the marginal odds ratio.

For the underlying estimation of the binary outcome variable in each treatment arm, the following baseline covariates will be utilized:

- Actual baseline ordinal score
- Age (continuous)
- Sex
- Race and Ethnicity (Black or Hispanic indicator)
- Baseline CRP
- Baseline lymphocyte count
- Baseline D-dimer
- Baseline creatinine
- Use of dexamethasone
- Chronic respiratory disease
- Chronic kidney disease
- Cardiovascular disease
- Comorbidities (Indicator for 2 or more comorbidities)

The following super learner libraries with logistic link functions will be applied:

- SL.glm (generalized linear model)
- SL.gam (general additive model using smoothing splines of degree 2 for continuous variables)
- SL.glmnet (generalized linear model with Lasso regularization, deviance as loss function and applying the lambda with minimal deviance for the prediction).

Categorical covariates with 90% of the subjects in one category will be dropped from the TMLE analysis. Mean imputation will be used for subjects missing values for continuous baseline variables. Missing values for categorical variables will be given a value of 'No'. No missing data is expected for baseline ordinal score

Odds ratio (treatment vs. placebo) = marginal odds ratio comparing the odds of patients with treatment vs. placebo in terms of who survived without ventilation up to and including Study Day 29.

Marginal odds ratios, corresponding 95% CIs, and a p-value from an TMLE will be presented. Additionally, marginal risk differences with corresponding 95% CI will be presented.

Missingness in the outcome is accounted for in the estimation procedure of TMLE using the missing indicator as shown in the below pseudocode. The TMLE approach will be implemented using the tmle R package (<https://cran.r-project.org/web/packages/tmle/index.html>).

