**Pseudo code:**

```

Y = binary outcome variable (that can include missing values)
trt = treatment information coded as 0, 1
BaselineCov = Dataframe of baseline covariates (numerical) of each
patient.
MissingIndicator = Vector with 1 indicating that outcome was missing, 0
otherwise
SL.library = c("SL.glm", "SL.gam", "SL.glmnet")

tmResult = tmle(Y = Y, A = trt, Delta = MissingIndicator, W =
BaselineCov, family = "binomial", Q.SL.library = SL.library,
g.SL.library = SL.library, Delta.SL.library = SL.library)

```

As a secondary analysis of the primary endpoint, marginal odds ratios, risk differences, and p-value calculated using TMLE will also be provided. If results from the primary analysis substantially differ between the logistic regression and TMLE, an assessment of the logistic regression model fit will be explored (including testing the model fit based on Nattino et al. [3]).

The proportion of subjects with baseline ordinal score 5 or 6, who survived without mechanical ventilation including Study Day 29 will be presented by Lenzilumab + RDV long with 95% CIs obtained from logistic regression with bootstrap as described in Section 6.1 for the logistic regression rows or using TMLE for the TMLE row.

Results of the sensitivity, secondary, and subgroup analyses for this endpoint will also be presented in [Table 4](#) for subjects in the primary subgroup.

Refer to [Table 1](#) for a list of covariates and subgroup analyses for this endpoint. Refer to [Table 2](#) for imputation methods to be applied to this endpoint.

A tipping point analysis that systematically and comprehensively varies assumptions about the missing outcomes on the two treatment arms will be performed. This tipping point analysis will vary assumptions about the missing outcomes on the two arms independently. The goal is to explore the plausibility of missing data assumptions under which the conclusions regarding efficacy change. Different scenarios will be explored that vary the assumed event rate among missing data to take values 1, 5, 10, 15, 20, 40% for the active treatment group ( $P_T$ ) and for the placebo group ( $P_P$ ). For each scenario, draws from the binomial distribution with parameter  $P_T$  for subjects in the active treatment group with missing outcome and draws from the binomial distribution with parameter  $P_P$  will be done for subjects in the placebo group missing outcome. This

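### The TMLE pseudocode passes a flag coded 1 = missing to an argument that marks observed outcomes, so both TMLE secondary analyses would most likely fail as written

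*SAP*

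**What the plan says.** SAP 6.5.2 (Targeted Maximum Likelihood Method) gives the code for the TMLE analyses of the primary endpoint. The outcome vector is "Y = binary outcome variable (that can include missing values"). The flag is "MissingIndicator = Vector with 1 indicating that outcome was missing, 0 otherwise", and it goes straight into the call: "tmResult = tmle(Y = Y, A = trt, Delta = MissingIndicator, W = BaselineCov".

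SAP 8.1.3 (Secondary Analysis for the Primary Endpoint) repeats the definition and the call, "tmResult = tmle(Y = Y, A = trt, Delta = MissingIndicator, W", and points the reader to that code: "Missingness in the outcome is accounted for in the estimation procedure of TMLE using the missing indicator as shown in the below pseudocode".

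There are two TMLE approaches, and 6.5.2 names the tmle R package for both.

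- **First approach:** every missing outcome is handled through the flag.
- **Second approach:** discharged subjects with a missing outcome count as non-events, and those lost while hospitalized or transferred are multiply imputed. The flag is left with one group: "Event for subjects with no post-baseline data will be missing and handled using TMLE".

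No other part of the SAP reverses the flag or gives Delta a different meaning.

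**The concern.** TMLE with missing outcomes needs an indicator that picks out the records with a known outcome. The outcome model is fitted on those records, the probability of being observed is modelled for everyone, and the targeting step again uses the observed records. Delta is that indicator. A flag with 1 for missing picks out the complement.

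Two things are at stake:

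- The two TMLE rows of Table 4, with their odds ratio, risk difference and p-value. Section 8.1.3 bases the test decision of this secondary analysis on the p-value of the marginal odds ratio.
- The comparison of logistic regression with TMLE. Under 8.1.3 a substantial difference between them prompts an exploration of the logistic model's fit.

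Section 8.2.3 repeats the 8.1 analysis in all ITT and mITT subjects, in tables of the same format. Any TMLE rows produced there would carry the same error.

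**Working it through.** The plan states no figure on this point, so the check is a trace of the flag followed by an illustration.

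**Trace**

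1. Outcome missing: Y has no value and MissingIndicator = 1, so Delta = 1.
2. Outcome known: Y is 0 or 1 and MissingIndicator = 0, so Delta = 0.
3. TMLE fits the outcome regression and the targeting step on records with Delta = 1. By line 1, none of these has a value of Y.
4. Under the second approach, Delta = 1 holds only for subjects with no post-baseline data. If there are none, the set is empty.

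The trace gives the same result at any missing rate.

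**Inputs for the illustration**

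- Subgroup size: 400 (SAP section 5), taken as 200 per arm.
- Control event rate: 16%, with odds ratio 2.5 (SAP section 5). Treated odds = (0.16/0.84)/2.5 = 0.0762, so the treated rate = 0.0762/1.0762 = 7.1%, which agrees with the plan's 7%. On the event scale the planning odds ratio, treated versus control, is 1/2.5 = 0.40.
- Missing outcomes: the SAP says only that few are expected. Rates of 1%, 3%, 5% and 10% are assumptions.

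A TMLE was coded directly for this check, with logistic models for outcome, treatment and missingness, one baseline covariate, and a logistic targeting step. It was run on 300 simulated data sets per missing rate, skipping any with no missing outcome. Each data set was analysed once with Delta as printed and once with Delta = 1 - MissingIndicator. The table describes the first approach.

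| Assumed missing | Delta = 1 as printed (400 x rate) | Outcome values among them | Known outcomes left out | Reversed flag: median odds ratio | Reversed flag: median risk difference |
|---|---|---|---|---|---|
| 1% | 4 | 0 | 396 | 0.397 | -0.088 |
| 3% | 12 | 0 | 388 | 0.415 | -0.083 |
| 5% | 20 | 0 | 380 | 0.409 | -0.085 |
| 10% | 40 | 0 | 360 | 0.412 | -0.086 |

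As printed, the selected set contained no outcome value in any simulated data set, so the outcome model could not be fitted. With the flag reversed, the median odds ratio is 0.40 to 0.42, in line with the planning value of 0.40.

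The simulation shows what follows from the convention that Delta = 1 means observed. It does not test that convention, because it builds it in. The tmle package was not available, so how its own call would respond is untested.

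**The case against.** The strongest objection is that neither document defines Delta, and that the simulation assumes the meaning in dispute. The package was not run, so its interface has not been verified here. That limit stands. It does not rescue the code, because an outcome regression cannot be fitted where the outcome is unknown, and Delta = 1 for observed is the standard convention of the method the SAP names.

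A second objection is that the block is labelled as pseudocode and the surrounding text makes the intent plain: to adjust for missing outcomes from baseline covariates and treatment. Other blocks are also not executable as printed. The CLASS statement in 6.5.1.3 has a stray semicolon, and the final data step there stacks the unreplicated complete-data file instead of the replicated one just created. This is fair, and it lowers the severity. But the flag is an explicit instruction, printed identically twice, and the intent is met only by departing from it.

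Some stronger readings are tempting, and the documents do not support them:

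- **A plausible but wrong TMLE result would be reported.** No route to one has been shown. With no outcome values to fit, a visible failure at first programming is the likelier result.
- **The efficacy conclusion or type I error is at risk.** The primary test is the logistic regression with multiple imputation (8.1.1). TMLE is outside the hierarchy in 6.8. The tipping-point analysis does not use it.
- **TMLE decides whether the primary model is adequate.** Section 8.1.3 says only that a substantial difference leads to an exploration of fit.
- **The 12 and 388 split at 3% describes both approaches.** It rests on an assumed rate and fits the first approach only.

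**Conclusion.** The flag is reversed relative to Delta in both printed copies. Followed literally, the records selected for fitting hold no outcomes, and both TMLE secondary analyses of the primary endpoint would most likely fail to run or give meaningless estimates. Under the second approach the selected set may be empty.

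What is lost is the TMLE rows of Table 4 and the comparison that prompts the exploratory fit assessment. The severity is moderate: the plan is wrong as written, but in a secondary analysis.

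The conclusion rests on the standard meaning of Delta in TMLE and not on a run of the package. It does not depend on the missing rate. The record counts do, and they are illustrative.

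**What to change.** In SAP 6.5.2 and 8.1.3, replace the flag with ObservedIndicator = 1 if the Day 29 outcome is known and 0 if it is missing, and pass Delta = ObservedIndicator (equivalently, 1 - MissingIndicator). Before unblinding, run the call on simulated data with known missingness. Include a second-approach case in which no subject lacks post-baseline data.

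The cost is one line of code in two places and a short test. Endpoint, sample size and testing order do not change. Correcting it now also avoids settling the repair after results are known.
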